### 8.1.1. Permanent Discontinuation from Study Treatment

Subjects who discontinue the investigational product early will continue in the study according to the Schedule of Activities (Section 2).

Investigational product is to be discontinued for patients who experience clinically significant systemic hypersensitivity events (such as anaphylaxis) following administration of investigational product.

### 8.2. Discontinuation from Study

Some possible reasons that may lead to permanent discontinuation include:

- AE
  - If the investigator decides that the subject should be withdrawn because of an AE/SAE or a clinically significant laboratory value, the investigational product is to be discontinued and appropriate measures are to be taken. Lilly or its designee is to be alerted immediately. Refer to Safety Evaluations, Sections 9.2 and 9.2.1.
- subject experiences a systemic hypersensitivity event (such as anaphylaxis) following administration of investigational product.
- subject becomes pregnant

Leo Document ID = 723d17a2-8adb-4d94-8c62-013049e7ef78

Approver: [REDACTED]  
Approval Date & Time: 21-Aug-2018 12:34:29 GMT  
Signature meaning: Approved

Approver: [REDACTED]  
Approval Date & Time: 21-Aug-2018 17:32:39 GMT  
Signature meaning: Approved

4.1. Primary Objective

To test the hypothesis that treatment with LY3074828 is superior to placebo in inducing PASI 90 response at Week 16 in subjects with moderate-to-severe plaque psoriasis

4.2. Secondary Objectives

- To evaluate the safety and tolerability of treatment with LY3074828
- To evaluate the efficacy of treatment with LY3074828 compared to placebo in inducing PASI 100 and PASI 75 at Week 16
- To evaluate the efficacy of treatment with LY3074828 compared to placebo in inducing sPGA 0 (clear) and sPGA 0/1 at Week 16
- To evaluate the effect of LY3074828 on patient reported outcome measures: Psoriasis Symptom Scale, Patient Global Assessment, DLQI, and SF-36 at Week 16
- To characterize the long-term efficacy of LY3074828 on the PASI 100, PASI 90, and PASI 75 responses at Week 52, 104, and 120
- To characterize the long-term efficacy of LY3074828 on patient reported outcome measures Psoriasis Symptom Scale, Patient Global Assessment, DLQI, and SF-36 at Weeks 52, 104, and 120
- To characterize the PK of LY3074828.

4.3. Exploratory Objectives

- To characterize the loss of response during the Maintenance Period (if applicable) for subjects who achieve PASI 100 at Week 16
- To characterize the loss of response during the Maintenance Period (if applicable) for subjects who achieve PASI 90 at Week 16
- To characterize the ability of retreatment (if applicable) with LY3074828 to regain PASI 100 for subjects who achieve PASI 100 response at Week 16 and experience loss of response during the Maintenance Period
- To characterize the ability of retreatment (if applicable) with LY3074828 to regain PASI 90 for subjects who achieve PASI 90 response at Week 16 and experience loss of response during the Maintenance Period
- To evaluate the efficacy of treatment with LY3074828 in inducing PASI 100, PASI 90, PASI 75, and mean PASI improvements at all time points evaluated
- To evaluate the efficacy of treatment with LY3074828 in inducing mean BSA improvements at all time points evaluated
- To evaluate the efficacy of treatment with LY3074828 in inducing sPGA 0 and sPGA 0/1 at all time points evaluated

- To evaluate the efficacy of treatment with LY3074828 in PSSI at all time points evaluated
- To evaluate the efficacy of LY3074828 on patient reported outcome measures: Psoriasis Symptom Scale, Patient Global Assessment, DLQI, and SF-36 at all time points evaluated
- To evaluate the psychometric properties of the Psoriasis Symptom Scale including validity, reliability, and responder definition
- To evaluate the relationships between LY3074828 exposure, biomarkers, and efficacy
- To evaluate the development of anti-drug antibodies for LY3074828.

5. Study Design

5.1. Summary of Study Design

Study AMAF is a multicenter, randomized, parallel-arm, placebo-controlled trial with 4 study periods in subjects with moderate-to-severe plaque psoriasis.

[figure not shown]
Screening Period (≤4 weeks): Subjects will be evaluated for study eligibility ≤28 days before the baseline visit (Visit 2/Week 0). At the baseline visit (Visit 2), subjects who fulfill the eligibility criteria will be randomized to 1 of 4 induction treatment arms.

Induction Period (16 weeks): A double-blind, 16-week Induction Period is designed to establish the efficacy and safety of LY3074828 administered at Visit 2 (Week 0) and Visit 5 (Week 8). Subjects will be randomized to 1 of 4 induction treatment arms (LY3074828 30 mg SC, LY3074828 100 mg SC, LY3074828 300 mg SC, and placebo every 8 weeks [Q8W]) stratified on the basis of previous exposure to biologic therapy for treatment of psoriasis.

Maintenance Period (88 weeks): The Maintenance Period consists of 88 weeks of treatment. At the end of the Induction Period (Week 16), subjects will continue treatment in the Maintenance Period which is intended to explore 1 of 2 treatment strategies through Week 104. All placebo subjects and subjects assigned to treatment with LY3074828 who have a <90% improvement in Psoriasis Area and Severity Index (PASI) from baseline (PASI 90) at Week 16 will receive LY3074828 300 mg SC Q8W during the entire Maintenance Period. Subjects with ≥PASI 90 PRN dosing group) at Week 16 will only be dosed with LY3074828 at the baseline dose level assignment no more frequently than Q8W when disease activity level is <PASI 90, and this will continue until ≥PASI 90 is regained.

Follow-up Period (16 weeks): The Follow-up Period will include a visit every 4 weeks for a total of 16 weeks following Visit 29 to assess subject safety and study drug efficacy.

[Figure 5.1](#) illustrates the study design.

^a Visits will occur every 4 weeks in the Maintenance and Follow-up Periods.
 Abbreviations: PASI = Psoriasis Area and Severity Index; PRN = as needed; Q8W = every 8 weeks.

Figure 5.1. Illustration of study design for Clinical Protocol I6T-MC-AMAF.

5.2. Determination of Sample Size

Approximately 200 subjects will be randomized at a 1:1:1:1 ratio in the blinded induction dosing period to LY3074828 30 mg, 100 mg, 300 mg, and placebo (50 subjects per dosing regimen, respectively). Randomization will be stratified by prior exposure to biologic therapy for psoriasis (yes/no).

Assuming 60% and 3% PASI 90 response rates at 16 weeks for LY3074828 and placebo, respectively, pairwise comparisons to placebo have over 99% power using a 2-sided Fisher's exact test at the 0.05 significance level, with no adjustment for multiple comparisons.

As results for PRN dose arms in the Maintenance Period will support the maintenance dosing strategy in Phase 3 planning, a reasonable total number of subjects who completed 1-3 visits in the Maintenance Period (Week 20 to Week 28) will be needed. Based on study simulations under the treatment effect scenario outlined above, approximately 49 subjects (9 on 30 mg, 18 on 100 mg, 22 on 300 mg PRN arms) will have completed the Week 20 visit at the time of the primary endpoint datalock.

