### **10.3.7. Interim Analyses**

There will be an interim database lock after all subjects complete the primary endpoint at Week 16 (Visit 7). CCI

Interim analyses will not impact the current study design or implementation. The interim efficacy results will be used for internal decision making to trigger planning activities associated with the investigational product and to aid development of PK/PD modeling. No adjustment of Type I error will be performed.

Given that the additional interim database locks are post-primary, these additional analyses will not impact the primary analysis and outcomes. All post-primary interim analyses are exploratory and supportive in nature, and do not impact the integrity or scientific value of this study.

To minimize any bias being introduced into the analysis of the study results, the SAP and PK/PD analysis plan will be finalized and approved before the first efficacy interim analysis begins. Unblinding details are specified in the unblinding plan section of the SAP or in a separate unblinding plan document. Information that may unblind the study during the analyses will not be reported to study sites or the blinded study team until the study has been unblinded.

Ongoing monitoring of safety data (including AEs, SAEs, and selected laboratory measurements) will continue throughout the study using blinded data. Interim safety analyses may be conducted to review unblinded safety data; the analyses will be conducted and reviewed by an internal assessment committee composed of personnel who do not have direct site contact, data entry responsibilities, or data validation responsibilities. Details regarding safety reviews will be specified in the trial level safety review plan or a separate document.

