5.3. Method of Assignment to Treatment

This study involves a comparison of SC administration of LY3074828 versus placebo during a 16-week Induction Period followed by a Maintenance Period designed to explore PRN maintenance treatment based upon disease activity at the end of the Induction Period. A Rescue Period is also available for subjects who received PRN treatment. [Table 5.1](#) shows the treatment regimens.

Table 5.1. Treatment Regimens in Induction, Maintenance and Rescue Periods

Treatment Group	Description		
	Induction Period	Maintenance Period	Rescue Period
LY Dose Arm 1	30 mg LY SC Q8W	If <PASI 90 at Week 16: 300 mg LY given SC Q8W	
		If ≥PASI 90 at Week 16: 30 mg LY given SC PRN	30 mg LY SC PRN to 300 mg LY SC Q8W
LY Dose Arm 2	100 mg LY SC Q8W	If <PASI 90 at Week 16: 300 mg LY given SC Q8W	
		If ≥PASI 90 at Week 16: 100 mg LY given SC PRN	100 mg LY SC PRN to 300 mg LY SC Q8W
LY Dose Arm 3	300 mg LY SC Q8W	If <PASI 90 at Week 16: 300 mg LY given SC Q8W	
		If ≥PASI 90 at Week 16: 300 mg LY given SC PRN	300 mg LY SC PRN to 300 mg LY SC Q8W
Placebo	Placebo SC Q8W	300 mg LY given SC Q8W	

Abbreviations: LY = LY3074828; PASI = Psoriasis Area and Severity Index; PASI 90 = 90% improvement in PASI from baseline; PRN = as needed; Q8W = every 8 weeks; SC = subcutaneous.

6. A Priori Statistical Methods

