Appendix 1. Simulation for Logistic Regression with Firth Correction

When PBO response rate is small and there are zero cell values, logistic regression will over estimate variance resulting in larger *p*-values and reduced power. Logistic regression with a Firth correction adjusts for small sample sizes and zero cell values. We used simulation to investigate a “two-step” approach. If there is

- “Small” number of PBO responders, then use logistic regression with Firth correction
- “Not Small” number of PBO responders, then use logistic regression without correction

LY Response Rate	Treatment Effect (LY-PBO)	Single Analysis Power		“Two-Step” Approach Power			
		Logistic Regression	Logistic Regression w/ Firth Correction	≤1 PBO Responder	≤2 PBO Responder	≤3 PBO Responder	≤4 PBO Responder
0.03	0.00	<0.001	<0.001	<0.001	<0.001	<0.001	<0.001
0.05	0.02	0.002	0.002	0.002	0.002	0.002	0.002
0.10	0.07	0.063	0.075	0.075	0.075	0.075	0.075
0.15	0.12	0.277	0.363	0.372	0.369	0.363	0.363
0.20	0.17	0.535	0.683	0.695	0.694	0.684	0.683
0.25	0.22	0.709	0.892	0.901	0.899	0.893	0.893
0.30	0.27	0.783	0.981	0.984	0.984	0.982	0.982
0.35	0.32	0.793	0.993	0.994	0.994	0.993	0.993
0.40	0.37	0.798	0.999	0.999	0.999	0.999	0.999
0.45	0.42	0.798	0.999	0.999	0.999	0.999	0.999
0.50	0.47	0.799	>0.999	>0.999	>0.999	>0.999	>0.999
0.55	0.52	0.799	>0.999	>0.999	>0.999	>0.999	>0.999
0.60	0.57	0.799	>0.999	>0.999	>0.999	>0.999	>0.999

Results showed that logistic regression with Firth correction increased the power by ~10% compared to the ones without Firth correction when the treatment difference is >7%. Therefore, it is suggested to apply Firth correction in the logistic regression models in Study AMAF.

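### SAP 5.2: one 60% PASI 90 rate for all doses cannot produce the 9/18/22 PRN split credited to it, and that split does not support over 99% power for 30 mg

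*SAP*

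**What the plan says.** The second paragraph of SAP 5.2 gives one active rate and one placebo rate: "Assuming 60% and 3% PASI 90 response rates at 16 weeks for LY3074828 and placebo" respectively. With 50 subjects per arm it concludes that "pairwise comparisons to placebo have over 99% power using a 2-sided" Fisher's exact test at 0.05, unadjusted. No dose is singled out.

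The third paragraph turns to maintenance data available at the primary lock. "Based on study simulations under the treatment effect scenario outlined above", it expects "approximately 49 subjects (9 on 30 mg, 18 on 100 mg, 22 on 300 mg PRN arms") who "will have completed the Week 20 visit at the time of the primary endpoint datalock". The only treatment-effect scenario above that sentence is 60% against 3%.

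Entry to a PRN arm depends on response. SAP Table 5.1 reads, for the lowest dose, "If ≥PASI 90 at Week 16: 30 mg LY given SC PRN", with the same rule for the other two doses. Protocol 10.3.7 sets one lock for the whole study: "There will be an interim database lock after all subjects complete the primary endpoint at Week 16 (Visit 7").

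**The concern.** The two paragraphs claim one scenario, yet the PRN counts rise steeply with dose. If every dose has the same response rate and the same number randomised, the expected PRN counts should be equal. Either 60% is not the rate assumed for every dose, or the counts do not come from the scenario named.

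The primary endpoint is tested for each dose separately against placebo (Protocol 10.3.3.1; SAP Table 6.3). If the simulation used a much lower 30 mg rate, the blanket power statement does not describe the 30 mg comparison. A reader who relies on it would take a non-significant 30 mg result as stronger evidence against that dose than the design can give. If the counts are wrong instead, the error lies in the projection that SAP 5.2 offers as support for planning Phase 3 maintenance dosing.

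**Working it through.** **Inputs.** From SAP 5.2: 50 per arm, 1:1:1:1 allocation, placebo rate 3%, active rate 60%, two-sided Fisher's exact test at 0.05, PRN counts 9, 18 and 22 (total 49). From SAP Table 5.1: PRN entry requires PASI 90 at Week 16.

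**Step 1: the plan's own figure.** All 51 × 51 outcomes were enumerated, rejecting where the two-sided Fisher p-value is at most 0.05. At 60% against 3%, power exceeds 99.999%. The stated figure reproduces.

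**Step 2: the split under a common rate.** The expected PRN count in an arm is 50 × p × f, where p is the Week 16 PASI 90 rate and f is the share of responders past Week 20 at the lock. The SAP does not give f. With equal allocation and one lock date it is taken as the same in each arm (an assumption) and cancels in ratios. A common p then gives 49/3 = 16.3 per arm, not 9/18/22.

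**Step 3: what the counts imply.** The rate ratio of 30 mg to 300 mg is 9/22 = 0.41, and of 100 mg to 300 mg 18/22 = 0.82. The counts fix only ratios, so the 30 mg rate depends on what the 60% stands for. If 60% were the 30 mg rate, the 300 mg rate would be 60% × 22/9 = 147%, which is impossible. Four other readings are possible. The ranges let each count vary by half a subject.

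| 60% stands for | Implied 30 mg rate | Exact Fisher power, 30 mg vs 3% | Implied f |
|---|---|---|---|
| 300 mg rate | 60% × 9/22 = 24.5% (22.7–26.5%) | 86% (80–91%) | 22/30 = 73% |
| mean of 100 and 300 mg | 60% × 9/20 = 27.0% (24.9–29.2%) | 92% (87–95%) | 20/30 = 67% |
| 100 mg rate | 60% × 9/18 = 30.0% (27.6–32.6%) | 96% (93–98%) | 18/30 = 60% |
| three-dose mean | 60% × 9/16.33 = 33.1% (30.9–35.3%) | 98.3% (96.9–99.1%) | 16.33/30 = 54% |

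The lowest implied 100 mg rate is 60% × 18/22 = 49.1%, so 100 and 300 mg stay above 99.9% power in all four readings.

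**Step 4: what 99% would need.** Power of 99% requires a 30 mg rate of about 34.8%. At 9:18:22 that means 34.8% × 18/9 ≈ 70% on 100 mg and 34.8% × 22/9 ≈ 85% on 300 mg (79–92% with rounding).

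**Step 5: the planned model.** The primary analysis is Firth-penalised logistic regression. SAP Appendix 1 gives it power of 0.892, 0.981 and 0.993 at active rates of 25%, 30% and 35%. Exact Fisher gives 0.874, 0.961 and 0.991 at those rates. The pattern is the same and the level slightly higher. Appendix 1 does not tie any rate to a dose.

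**Step 6: chance.** The text reports a simulation result, so sampling variation in one trial is not the issue. Even in a single trial with equal rates, 9 or fewer of 49 on 30 mg has probability 0.016 (binomial, 1/3).

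**The case against.** The power sentence is conditional, and on its condition it is correct. The SAP never says that 30 mg is expected to reach 60%, and Protocol 5.5 says the doses were picked to span minimal to maximal effect. On this view the only fault is a loose cross-reference. That describes how the inconsistency may have arisen, but it does not remove it: the statement covers the pairwise comparisons without exception, and the counts are credited to that same scenario.

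The size of the shortfall is less certain than its existence, and this part of the objection stands. None of the four readings is stated in the documents, and the passages that might settle the matter (Protocol 5.5 and 10.1) are redacted, which is not a fault in the plan. In the most favourable reading the gap is under one percentage point, and at its rounding extreme power reaches 99.1%. The planned Firth model does somewhat better than Fisher: at 30% the chance of a miss is 1.9%, not 3.9%.

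The harm is also limited. Odds ratios, treatment differences with 95% confidence intervals and linear trend tests are planned (SAP 6.1.3), and Appendix 1 already shows power falling at lower rates. A careful reader would not judge 30 mg on planning power alone.

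Unequal f could in principle explain the counts, but 30 mg would have to keep only about 41% as many responders past Week 20 as 300 mg. Nothing in the documents suggests that.

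**Conclusion.** The concern holds. The two paragraphs of SAP 5.2 cannot both describe a scenario with one 60% rate for every dose. The power arithmetic is sound at 60% against 3%. What fails is applying it to 30 mg alongside the 9/18/22 split.

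At the reported counts, the chance of missing significance at 30 mg is about 2% to 14% across the four readings (0.9% to 20% with rounding), where the stated power implies less than 1%. This rests on equal f across arms, a true placebo rate of 3% and 50 subjects per arm. The exact 30 mg power cannot be read from the documents, so these figures are a range and not an estimate. The 100 and 300 mg comparisons are unaffected.

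**What to change.** In SAP 5.2, give the Week 16 PASI 90 rate for each dose used in the simulation that produced 9/18/22, and the power for each dose at those rates. Limit the claim of over 99% to the doses for which it holds, and name the simulation scenario in place of the reference back to the preceding paragraph. Suggested wording:

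> At assumed Week 16 PASI 90 rates of [x]%, [y]% and [z]% for 30, 100 and 300 mg and 3% for placebo, power is [a]%, [b]% and [c]% (two-sided Fisher's exact test, 0.05).

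If 60% is truly assumed for every dose, keep the power statement and correct the PRN counts, to about 16 per arm if the total of 49 stands.

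The cost is SAP wording only, with no change to sample size or test. The stated power for 30 mg may become less favourable.

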5.3. Method of Assignment to Treatment

This study involves a comparison of SC administration of LY3074828 versus placebo during a 16-week Induction Period followed by a Maintenance Period designed to explore PRN maintenance treatment based upon disease activity at the end of the Induction Period. A Rescue Period is also available for subjects who received PRN treatment. [Table 5.1](#) shows the treatment regimens.

Table 5.1. Treatment Regimens in Induction, Maintenance and Rescue Periods

Treatment Group	Description		
	Induction Period	Maintenance Period	Rescue Period
LY Dose Arm 1	30 mg LY SC Q8W	If <PASI 90 at Week 16: 300 mg LY given SC Q8W	
		If ≥PASI 90 at Week 16: 30 mg LY given SC PRN	30 mg LY SC PRN to 300 mg LY SC Q8W
LY Dose Arm 2	100 mg LY SC Q8W	If <PASI 90 at Week 16: 300 mg LY given SC Q8W	
		If ≥PASI 90 at Week 16: 100 mg LY given SC PRN	100 mg LY SC PRN to 300 mg LY SC Q8W
LY Dose Arm 3	300 mg LY SC Q8W	If <PASI 90 at Week 16: 300 mg LY given SC Q8W	
		If ≥PASI 90 at Week 16: 300 mg LY given SC PRN	300 mg LY SC PRN to 300 mg LY SC Q8W
Placebo	Placebo SC Q8W	300 mg LY given SC Q8W	

Abbreviations: LY = LY3074828; PASI = Psoriasis Area and Severity Index; PASI 90 = 90% improvement in PASI from baseline; PRN = as needed; Q8W = every 8 weeks; SC = subcutaneous.

6. A Priori Statistical Methods

6.1. General Considerations

Statistical analysis of this study will be the responsibility of Eli Lilly and Company (hereafter Lilly). The statistical analyses will be performed using SAS® Version 9.4 or higher.

Continuous data will be summarized in terms of the number of observations, mean, standard deviation (SD), minimum, median, and maximum. The minimum and maximum will be reported to the same number of decimal places as the raw data recorded in the database. The mean and median will be reported to 1 more decimal place than the raw data recorded in the database. The SD will be reported to 2 more decimal places than the raw data recorded in the database. In general, the maximum number of decimal places reported shall be 4 for any summary statistic.

Categorical data will be summarized in terms of the number of patients in the analysis population, the number of patients providing data at the relevant time point, frequency counts, and the percentages corresponding to the appropriate method. Percentages will be presented to 1 decimal place. Percentages will not be presented for zero counts.

All confidence intervals (CIs) and statistical tests will be 2-sided unless otherwise specified. P-values which are greater than or equal to 0.001, and less than or equal to 0.999, will be presented to 3 decimal places. All other p-values which are less than 0.001 will be presented as <0.001, while p-values greater than 0.999 will be presented as >0.999. Confidence intervals will be presented to 1 more decimal place than the raw data.

6.1.1. Subject Populations for Analyses

For purposes of analysis, populations for analyses are described in [Table 6.1](#).

Table 6.1. Subject Populations for Analyses

Population	Description
Intent-to-treat (ITT) (Induction Period Efficacy)	All randomized subjects, even if the subject does not take the assigned treatment, does not receive the correct treatment, or otherwise does not follow the protocol: 
 Unless otherwise noted, efficacy and health outcomes analyses for the Induction Period will be conducted on this population. Subjects will be analyzed according to the treatment to which they were assigned.
Induction Period Safety	All randomized subjects who received at least 1 dose of study treatment: 
 Unless otherwise noted, safety analyses for the Induction Period will be conducted on this population. Subjects will be analyzed according to the treatment to which they were assigned.
Maintenance Period Efficacy	All randomized subjects who have entered the Maintenance Period (see definition of entering Maintenance Period in Section 6.1.2.1): 
 Unless otherwise noted, efficacy, and health outcomes for the Maintenance Period will be conducted on this population. Subjects will be analyzed according to the treatment to which they were assigned in Maintenance Period.

Population	Description
Maintenance Period Safety	
All randomized subjects received at least 1 dose of study treatment who have entered the Maintenance Period (see definition of entering Maintenance Period in Section 6.1.2.1):
 
 • Unless otherwise noted, safety analyses for the Maintenance Period will be conducted on this population. • Subjects will be analyzed according to the treatment to which they were assigned in Maintenance Period, with all LY3074828 300 mg Q8W arms combined, that is, there will be 4 treatment groups in the Maintenance Period: 
 ○ LY 300 mg PRN ○ LY 100 mg PRN ○ LY 30 mg PRN ○ LY 300 mg Q8W (including subjects from 4 Induction Period treatment groups)
Rescue Period (Efficacy and Safety)	
All PRN subjects who received at least 1 dose of rescue treatment:
 
 • For subjects who didn't qualify for rescue treatment but get the rescue dose by mistake, they will still be included in the Rescue Period analysis population. • Unless otherwise noted, efficacy, health outcomes and safety endpoints for the Rescue Period will be analyzed on this population.
All Periods Safety	
All subjects who received at least 1 dose of LY3074828 treatment
 
 • Safety analysis will be analyzed for all subjects who were exposed to at least 1 dose of LY3074828 treatment • All LY3074828-exposed subjects will combined in the All Periods safety analysis

Abbreviation: ITT = intent-to-treat; PRN = as needed.

